4.7 Demographic and Other Baseline Characteristics

Age will be taken from the demographics form in the eCRF.

Demographic and other baseline characteristics will be listed for all participants and summarised for the FAS as:

- Demographics (age [years], age group [≥ 18 -<50, ≥ 50 -<65, ≥ 65 -<85, and ≥ 85 years], sex, race (if collected), country and ethnicity)
- Participant characteristics at baseline (height [cm], weight [kg], weight group [< 40 , ≥ 40 -<75, ≥ 75 -<90, ≥ 90 -<120, and ≥ 120 kg], body mass index [BMI], BMI group [Underweight (< 18.5 kg/m²), Normal weight (≥ 18.5 - < 25.0 kg/m²), Overweight (≥ 25.0 - < 30.0 kg/m²), Obese (≥ 30.0 kg/m²)], family history of premature cardiovascular disease [Y/N], and substance use [nicotine, alcohol, caffeine and drugs])
- Baseline disease characteristics:
 - T2DM diagnosis [Y/N] and T2DM duration [years] from medical history form in the eCRF
 - Derived CKD stage (eGFR category) [Stage 2 (60-89 mL/min/1.73m²)/Stage 3a (45-59 mL/min/1.73m²)/Stage 3b (30-44 mL/min/1.73m²)/Stage 4 (15-29 mL/min/1.73m²)/Stage 5 (< 15 mL/min/1.73m²)], eGFR (mL/min/1.73m²), albuminuria [defined as 150-5000 mg albumin/g creatinine, with a further categorisation of 'moderate albuminuria' for 150-300 mg albumin/g creatinine and

‘severe albuminuria’ for >300-5000 mg albumin/g creatinine; count and percentage of participants meeting criteria], UACR (mg/g)

- CKD diagnosis, including primary renal diagnosis [Cystic kidney disease, Diabetic nephropathy, Ischaemic/Hypertensive nephropathy, Chronic glomerulonephritis, Renal artery stenosis, Chronic pyelonephritis (infectious), Chronic interstitial nephritis, Obstructive nephropathy, Unknown, Other (Specify)] and chronic glomerulonephritis type [IgA nephropathy, Focal segmental glomerulosclerosis (FSGS), Membranous nephropathy, Minimal change (which is part of exclusion criteria 1), Lupus nephritis, Other primary or secondary glomerulonephritis (Specify)] from CKD diagnosis form in the eCRF
- Angiotensin-converting enzyme inhibitor (ACEi) history [Y/N]
- Angiotensin receptor blocker (ARB) history [Y/N]
- Mineralocorticoid receptor agonist (MRA) history [Y/N]

Medical history and surgical history will be coded using Medical Dictionary for Regulatory Activities (MedDRA) version 23.0 or later. The frequency and percentage of participants with each condition will be summarised by system organ class (SOC) and preferred term (PT). Participants with multiple unique terms will be counted once per each unique PT and unique SOC. A participant can have one or more PTs reported under a given SOC. Each summary will be sorted alphabetically by SOC and PT, unless otherwise stated.

By-participant listings of demographic data (including age, sex, race, baseline weight, baseline height and baseline BMI) and the baseline disease characteristics data detailed above will be provided.

4.8 Concomitant Medication

Any medication or vaccine (including over-the-counter or prescription medications, vitamins, and/or herbal supplements) that the participant is receiving on or after the date of first dose of randomised treatment (and could have started prior to or during treatment) will be recorded as concomitant. Medications starting after the date of discontinuation from study treatment/withdrawal from study will be listed but will not be classified or summarised. Medications completed prior to the date of first dose of randomised treatment will be listed but will not be classified or summarised.

If medication start and/or stop dates are missing or partial, the dates will be compared as far as possible with the date of first dose of randomised treatment. Medications will be assumed to be concomitant unless there is clear evidence (through comparison of partial dates) to suggest that the medication stopped prior to first dose of randomised treatment.

The medications and supplements listed below are prohibited from the time of consent and for the duration of the study. Participants taking any of these medications at the time of randomisation cannot be included into the study:

- SGLT2i.
- Direct renin inhibitor (e.g. Aliskiren).
- Cyclosporin or tacrolimus.
- Receiving cytotoxic therapy, immunosuppressive therapy, or other immunotherapy for primary or secondary renal disease within 6 months prior to screening.

In addition to the above, the following medications cannot be initiated or any changes to dose made after the participant has consented, and until the participant has completed the study (or discontinued / withdrawn participation):

- ACEi.
- ARB.
- Angiotensin receptor neprilysin inhibitor (ARNi).
- MRA.

A medical review will be performed to determine whether a medication is classified as prohibited and this medically reviewed classification of prohibited medications will be used for any outputs involving prohibited medications.

Concomitant medications will be summarised for the FAS by drug class and (generic) drug name. A summary table by drug class and generic drug name will be generated for each of the following:

- all allowed concomitant medication taken during the study
- prohibited concomitant medication taken during the study

A by-participant listing of concomitant medications at study entry and taken during treatment will be presented.

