6.5.1 Prohibited Concomitant Medications

The medications and supplements listed below are prohibited from the time of consent and for the duration of the study. Participants taking any of these medications at the time of randomisation cannot be included into the study:

- SGLT2i.
- Direct renin inhibitor (eg, Aliskiren).
- Cyclosporin or tacrolimus.
- Receiving cytotoxic therapy, immunosuppressive therapy, or other immunotherapy for primary or secondary renal disease within 6 months prior to screening.

In addition to the above, the following medications cannot be initiated or any changes to dose made after the participant has consented, and until the participant has completed the study (or discontinued / withdrawn participation):

- ACEi.
- ARB.
- ARNi.
- MRA.

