6.5.3 Background Standard of Care Therapy

Prescribed SoC treatment for CKD (eg, ACEi and/or ARB) should be stable for at least 4 weeks prior to screening (see inclusion criterion #4) and remain stable during the study.

It is preferable that any background medical therapy (eg, antidiabetic or antihypertensive therapy [including diuretics] or therapy with statins) does not change during study intervention; ie, between the screening visit and the last dose of investigational product. However, if this is necessary, the participant does not need to be withdrawn from study intervention.

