4.2 General Presentation Considerations

4.2.1 Study Period

The following study periods are defined (if the specified visit did not take place, the date for planned visit should be used):

- Overall study period – from date of Visit 1 to date of Visit 8
- Screening period – from date of Visit 1 up to the day before Visit 2; this can be up to approximately 4 weeks in duration prior to randomisation
- Treatment (Interventional) period – from date of Visit 2 to date of Visit 7
- On-treatment period – from the same date as the first administration of study intervention until the earliest of: 28 days after last dose of zibotentan/placebo and/or dapagliflozin/placebo; end of study; lost to follow-up; and withdrawal of consent
- Off-treatment period – from more than 28 days after the last dose of study intervention
- Follow-up period – from day after Visit 7 to date of Visit 8

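### The planned medication tables do not show new or increased diuretic use by arm: baseline and new use are pooled, dose increases do not appear, and drugs started after study drug is stopped are listed only.

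*SAP*

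**What the plan says.** **Diuretics may change.** Protocol 6.5.3 prefers that "antihypertensive therapy [including diuretics] or therapy with statins) does not change during study intervention". It then adds: "However, if this is necessary, the participant does not need to be withdrawn from study intervention". Protocol 6.5.1 is stricter for ACEi, ARB, ARNi and MRA: "the following medications cannot be initiated or any changes to dose made after the participant has consented". Among diuretics, then, only MRAs are frozen. The rest belong with the allowed medications.

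**What is tabulated.** SAP 4.8 counts a drug as concomitant if it is received on or after first dose, and says it "could have started prior to or during treatment". Two tables follow, both by drug class and generic name: one for prohibited medication and one for "all allowed concomitant medication taken during the study". SAP 4.8 does not mention arms, but Protocol 9.4.1 has all results presented by arm and overall.

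**Where the tables stop.** SAP 4.8: "Medications starting after the date of discontinuation from study treatment/withdrawal from study will be listed but will not be classified or summarised".

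**Where the fluid event stops.** SAP 4.2.1 runs the on-treatment period to the earliest of several dates, one of which is "28 days after last dose of zibotentan/placebo and/or dapagliflozin/placebo". SAP 4.11.5.1 uses the same limit for time at risk of a fluid event.

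**Baseline.** SAP 4.7 counts ACEi, ARB and MRA history, but no other diuretic.

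**The concern.** Fluid retention closed the 5 mg arms and is the main risk being watched at 1.5 mg. SAP 3.2.2.7 defines the fluid event only by BNP, or by site weight with body water, crossing a threshold. A participant whose oedema or weight gain is treated with a diuretic before a crossing may never be counted. A low count can therefore mean little retention, or retention that was treated. By-arm diuretic use is the natural aid to telling these apart, and three features of SAP 4.8 limit it:

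- Long-standing and new diuretic use share one count, and no baseline count is planned that would allow subtraction.
- A participant already on a diuretic whose dose is raised adds nothing to a count by class or name.
- A diuretic started after study drug is stopped is only listed. Protocol 7.1 requires stopping for heart failure and keeps the participant in follow-up, so treatment of that episode may fall after the cut-off while the fluid event is still being counted.

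**Working it through.** **Plan's own figure.** SAP 4.14 gives 150 evaluable participants per large arm and 10% drop-out: 150 / 0.9 = 166.7, so 167 by rounding up against 166 stated, which agrees to within one participant. 166 + 166 + 83 = 415, as stated. The arm size of 166 is used below. The documents give no figure for diuretic use or fluid-event rates.

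**1. Calendar windows (document rules only).** For last dose and discontinuation on day d, with follow-up to Day 98, on-treatment days = min(d + 28, 98). Days beyond the medication tables = on-treatment days − d.

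| Stop day | On-treatment days | Beyond the tables | Share |
|---|---|---|---|
| 22 | 50 | 28 | 56% |
| 43 | 71 | 28 | 39% |
| 64 | 92 | 28 | 30% |

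These are calendar days for early stoppers, not shares of diuretic starts. SAP 4.8 does not say whether its cut-off also applies to completers. If it does, the figure is 98 − 84 = 14 of 98 days (14%).

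**2. Pooling (assumed rates).** Let b be baseline diuretic use, equal in both arms, and s the start rate among baseline non-users before study drug is stopped. Any use in the pooled table = b + (1 − b)s. Assume s = 10% versus 4%, a ratio of 2.5:

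| b | Any use, 10% arm | Any use, 4% arm | Pooled ratio | Difference (points) |
|---|---|---|---|---|
| 20% | 28.0% | 23.2% | 1.21 | 4.8 |
| 30% | 37.0% | 32.8% | 1.13 | 4.2 |
| 40% | 46.0% | 42.4% | 1.08 | 3.6 |
| 50% | 55.0% | 52.0% | 1.06 | 3.0 |

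With 15% versus 5% (ratio 3.0), the pooled ratios are 1.33, 1.21, 1.14 and 1.10.

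**3. What pooling keeps.** Difference in any use = (1 − b)(s1 − s0). At b = 30%, 0.042 × 166 = 7.0 participants. Counted among non-users, 0.06 × (0.7 × 166) = 7.0. The absolute number of extra starters is the same.

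**4. What pooling loses.** As a measure of precision only (the plan tests no medication table), take the normal-approximation chance of a one-sided 5% result. The pooled table uses 166 per arm. The new-start table uses the non-users, 133 down to 83 per arm as b runs from 20% to 50%.

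- 10% versus 4%: pooled 0.26 down to 0.14; new starts 0.61 down to 0.45.
- 15% versus 5%: pooled 0.49 down to 0.23; new starts 0.86 down to 0.69.

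**5. What is absent.** If each participant counts once per class and name, a same-drug dose increase adds 0. A start after the stop date adds 0 by the rule in SAP 4.8. Adding a different diuretic would still show by generic name, though possibly not by class.

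**The case against.** The strongest reply is that treated fluid retention already reaches the by-arm tables by another route. Physical examinations at every visit assess peripheral oedema (Protocol 8.2.1). Under Protocol 8.3.5, new clinically relevant findings are adverse events, and the need for treatment is one consideration in judging whether a laboratory or vital-sign change is clinically relevant. SAP 4.11.2 and 4.11.3 tabulate AEs, SAEs, AEs leading to discontinuation and the fluid-overload SMQ, with AE tables for both the on-treatment and the on-plus-off-treatment periods. Home-weight alerts lead to a clinic visit (Protocol 8.2.2), and weight, body water and BNP are summarised by arm (SAP 4.10.4, 4.12.2). A low fluid-event count beside a high SMQ count would itself point to retention that was treated early or stayed below threshold.

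This largely stands and limits the point. What remains is that none of these outputs shows diuretic treatment, and that weight, body water and BNP can be lowered by it.

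Two further replies also stand. The BNP and weight criteria that force a stop (Protocol 7.1) closely match the fluid-event criteria, so after such a stop the event has generally been met and a later diuretic cannot mask it. The post-stop gap therefore matters mainly for heart failure, or other stops, without a measured crossing; a heart-failure stop should itself appear among AEs leading to discontinuation. And this is a gap in tabulation, not in data: dates, doses and reasons for use are collected (Protocol 6.5), and post-stop starts are listed. The mock shells are not available and could add an output, but the SAP text plans none.

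**Conclusion.** The point holds as a cheap improvement to the safety outputs. The planned by-arm tables do not show diuretic treatment of fluid retention directly: same-drug increases and starts after the stop date are not tabulated, and the contrast in first starts before stopping is blurred in ratio and precision. Under the assumed rates, ratios of 2.5 to 3.0 appear as 1.06 to 1.33. Those figures rest on assumed start rates and balanced baseline use of 20% to 50%. The calendar windows rest on the documents alone.

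Three stronger readings are tempting and not supported:

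- That pooling hides an arm difference in first starts. With balanced baseline use, the absolute difference is preserved.
- That the relative risk of the fluid event is distorted by SAP 4.8. Any uncounted early-treated retention follows from the event definition and permitted care. Its size and direction are unknown, and repairing the medication table would leave the relative risk unchanged.
- That 56% of the relevant information is lost. That is a calendar share for a participant stopping on Day 22, unscaled by how many stop or start a diuretic.

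The interim fluid rule in SAP Appendix B.2 is redacted, so nothing is concluded about it.

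**What to change.** In SAP 4.8 add one output, by arm, giving:

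- (a) participants using a non-MRA diuretic at baseline;
- (b) participants who start or increase a non-MRA diuretic during the on-treatment period of SAP 4.2.1, including after study drug is stopped, by recorded reason for use.

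Fix the drug list and the reason-for-use terms before unblinding. A composite of fluid event or diuretic start/increase for a fluid-related reason could be added to SAP 4.11.5.1, but it is optional and supplementary. The defined fluid event, patient care and the efficacy analyses do not change.

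The cost is one extra output, a blinded review of reasons for use (similar to the medical review SAP 4.8 already plans for prohibited medication), and partial overlap with the fluid-overload SMQ table. No new data collection is needed.

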4.9 Treatment Compliance

Treatment compliance will be assessed by direct questioning and counting returned zibotentan/placebo capsules and dapagliflozin/placebo tablets during the site visits and documented in the source documents and eCRF. Deviation(s) from the prescribed dosage regimen should be recorded in the eCRF.

A record of the number of zibotentan/placebo capsules and dapagliflozin/placebo tablets dispensed to and taken by each participant must be maintained and reconciled with study intervention and compliance records.

For all calculations of compliance below, dispensed and returned refers to capsules/tablets taken at clinic and at home.

The percentage treatment compliance for zibotentan/placebo will be calculated from the number of capsules returned as:

$$\frac{\text{Capsules dispensed} - \text{Capsules returned}}{\text{Capsules expected to be taken}} \times 100$$

The percentage treatment compliance for dapagliflozin/placebo will be calculated from the number of tablets returned as:

$$\frac{\text{Tablets dispensed} - \text{Tablets returned}}{\text{Tablets expected to be taken}} \times 100$$

The overall percentage compliance will be calculated from the number of capsules and tablets returned as:

$$\frac{\text{Total study treatment dispensed} - \text{Total study treatment returned}}{\text{Total study treatment expected to be taken}} \times 100$$

A participant is expected to take one capsule and one tablet each day while on study treatment as indicated by the dosage regimen in the CSP, such that interruptions could mean compliance of less than 100%. The number of capsules and/or tablets expected to be taken is based on the number of study days between every set of clinic visits from Visit 2 to the end of treatment/early discontinuation visit. For any visits where a participant is required to take study treatment in clinic, the study treatment would be included in the study treatment expected to be taken between the last visit and the current visit.

Participants taking $\geq 80\%$ and $\leq 120\%$ of planned study treatment are considered to be compliant.

Study compliance percentage for zibotentan/placebo, dapagliflozin/placebo and overall will be summarised for the FAS as follows:

- Descriptive statistics will be summarised by treatment arms and overall.
- Percent compliance will be categorised according to the following categories:
 - $< 80\%$ (drug non-compliance)
 - $\geq 80\%$ and $\leq 120\%$ (drug compliance)
 - $> 120\%$ (drug non-compliance)

A by-participant listing of treatment compliance data will be provided.

4.10 Efficacy Evaluation

4.10.1 Analysis and Data Conventions

4.10.1.1 Null Hypothesis for Primary Objective and Related Secondary Objective

This study is designed to test for superiority and assess the dose-response relationship. The null hypothesis for the primary treatment comparison will be that there is no difference between zibotentan 1.5 mg and dapagliflozin 10 mg in combination and dapagliflozin 10 mg monotherapy in UACR. The alternative hypothesis will be that there is a difference. Symbolically, this is expressed as follows:

$H(0): \mu(\text{zibotentan 1.5 mg and dapagliflozin 10 mg in combination}) = \mu(\text{dapagliflozin 10 mg monotherapy})$

$H(1): \mu(\text{zibotentan 1.5 mg and dapagliflozin 10 mg in combination}) < \mu(\text{dapagliflozin 10 mg monotherapy})$

Where μ represents the least squares mean change in log-transformed UACR from baseline to Week 12. A one-sided test with $\alpha=0.05$ will be used to test this hypothesis.

The null and alternative hypotheses for the secondary efficacy treatment comparison of the difference between zibotentan 0.25 mg and dapagliflozin 10 mg in combination and dapagliflozin 10 mg monotherapy in UACR will be the same as described above for the primary efficacy treatment comparison (with the treatment arms updated as required).

4.10.1.2 Multi-centre Studies

No per centre (where the term ‘centre’ defines each investigator site) summaries or analyses will be performed.

4.10.1.3 Examination of Subgroups

When subgroup analyses are performed, it will be by diabetes (DKD versus non-DM CKD) and by stratification eGFR (≤ 45 mL/min/1.73m² versus > 45 mL/min/1.73m²). No formal statistical testing will be performed within these subgroups.

4.10.2 Analyses of UACR Objectives

4.10.2.1 Primary Estimand for Primary Objective

The primary estimand is a hypothetical estimand such that the treatment effect is quantified in the optimal situation where any potential confounder is minimised. The analysis will be performed on the FAS. The endpoint being assessed is the change in log-transformed UACR from baseline to Week 12. Participants will be included in the analysis if they have a non-missing baseline and at least one non-missing post-treatment visit UACR measurement.

For the intercurrent events (ICEs), if a participant dies, prematurely discontinues study treatment, or uses prohibited medication, the UACR data are treated as missing after the event and no imputation will be performed. The summary measure being evaluated is the geometric mean reduction of UACR from baseline to Week 12.

The estimand is specified through the following definitions of population, variable, treatment condition, ICEs, and population-level summary:

Target population:	Defined by the inclusion/exclusion criteria.
Variable:	Change in log-transformed UACR from baseline to Week 12.
Treatment condition:	Zibotentan 1.5 mg combined with dapagliflozin 10 mg versus dapagliflozin 10 mg.
Intercurrent events:	Death, premature discontinuation from study treatment, or use of prohibited medication (Handled by hypothetical strategy i.e. UACR data are treated as missing after the event. Deaths are expected to be relatively few and will be handled in the context of missing data).
Population-level summary:	Difference in least squares mean change in log-transformed UACR from baseline to Week 12 between zibotentan 1.5 mg combined with dapagliflozin 10 mg and dapagliflozin 10 mg.

4.10.2.2 Primary Analysis of Primary Objective

The primary efficacy endpoint for this study is the change in log-transformed UACR from baseline to Week 12. As UACR is assumed to follow a log-normal distribution, it will be log-transformed for statistical analysis purposes. The mean log changes in UACR at Week 12 (\hat{Y}_1, \hat{Y}_2) for zibotentan 1.5 mg combined with dapagliflozin 10 mg and dapagliflozin 10 mg alone will be estimated using a mixed model repeated measures [MMRM] method (Weeks 3, 6, 9, and 12). The least squares means will be back transformed to give the geometric mean change from baseline to Week 12. The geometric means will be converted to percentage mean change for Week 12 from baseline on the original scale using the following formula:

$$(\text{GeoMean}(UACR_{\text{Week12-Baseline}}) - 1) \times 100$$

The change in UACR from baseline to Week 12 for zibotentan 1.5 mg combined with dapagliflozin 10 mg compared to the dapagliflozin 10 mg monotherapy arm will be presented as a geometric mean ratio. The analysis model will include the fixed categorical effects of CSP version (Amendment 2

versus pre-Amendment 2), diabetes (DKD versus non-DM CKD), treatment, visit, and treatment-by-visit interaction, plus baseline eGFR strata (≤ 45 versus > 45 mL/min/1.73 m²), log(UACR) and baseline log(UACR)-by-visit interaction. An unstructured covariance structure will be used for the within-participant errors. The denominator degrees of freedom will be estimated using the Kenward-Roger approximation. If the MMRM model does not converge using an unstructured covariance structure, the Toeplitz, first-order autoregressive or compound symmetric covariance structure will be used. If that does not resolve the convergence issues, the analysis will be altered to use an analysis of covariance (ANCOVA) with a missing at random (MAR) multiple imputation (MI) method implemented (Section 4.10.2.3).

The geometric means, along with the conversion to percentage, for change from baseline to Week 12 from the model, and the 90% confidence intervals will be presented. The geometric mean ratio, which is the back-transformed least squares mean difference in change from baseline to Week 12 between two treatment arms, will be converted to adjusted percentage mean change between treatment arms as follows:

$$[(\text{Geometric Mean Ratio} - 1) \times 100]$$

The geometric mean ratio and the adjusted percentage mean change between treatment arms, as specified above, and the 90% confidence interval will be presented.

UACR will be summarised by treatment arm and visit in terms of absolute values and percentage change from baseline.

A plot showing the percentage mean change from baseline in UACR over time within each treatment arm will be provided.

A by-participant listing of the UACR data will be provided.

Sensitivity analyses

The following sensitivity analyses will be performed:

- The mean log change from baseline in UACR at Week 12 for zibotentan 1.5 mg combined with dapagliflozin 10 mg and dapagliflozin monotherapy on the PPS, using a MMRM method as described above.
- A multiple imputation analysis if not used as the primary analysis; see Section 4.10.2.3 for details.
- A tipping point analysis, depending on the results of the multiple imputation analysis; see Section 4.10.2.4 for details.
- A jump to reference analysis; see Section 4.10.2.5 for details.

Subgroup analyses

A forest plot will present the least squares mean and 90% CI overall and for each subgroup individually. The overall least square means will be taken from the primary analysis model and the subgroup least squares means will be taken from models including treatment arm by diabetes (DKD versus non-DM CKD) and treatment arm by stratification eGFR (below or equal versus above 45 mL/min/1.73m²), respectively. Homogeneity assessments between the DKD and the non-DM CKD sub-populations, and between the stratification eGFR below or equal to 45 mL/min/1.73m² and the stratification eGFR above 45 mL/min/1.73m² sub-populations, will be performed by visual inspection of the subgroups in the forest plot and by assessing the interaction p-values from the models.

